3.0 Outcome measures and mobile application

3.1 Primary outcome measures

3.1.1 The Neuropsychiatric Inventory Questionnaire – (NPI-Q): was developed as a more clinically relevant version of the original neuropsychiatric inventory. It is a self-administered questionnaire completed by a person who cares for a patient with AD or dementia. There are 12 domains in the NPI-Q each focused on a different and specific BPSD. The domains are as follows: delusions, hallucinations, agitation/aggression, depression/dysphoria, anxiety, elation/euphoria, apathy/indifference, disinhibition, irritability/lability, motor disturbance, nighttime behaviors and appetite/eating. Each is noted as present “yes” or absent “no”. If the informant answers “yes” to a symptom question they then are asked follow up questions on the symptom severity (mild, moderate, severe) and the amount of distress the symptoms causes them (the caregiver) on a 5-point scale¹⁹. On average the NPI-Q takes 5 minutes to complete.

3.1.2 The Brain CareNotes mobile application (BCN): was developed by Regenstrief Institute investigators Drs. [name], [name] and [name], and [name]. BCN takes all of the questions of the NPI-Q and delivers the questions from the scale to the caregiver through a smartphone mobile app that pings the caregiver on their phone at a set frequency, prompting the caregiver to complete the questionnaire. The app is designed for ecological momentary assessment (EMA) and is HIPPA compliant with secure transfer of data from the app to a secure cloud-based database. Ecological

momentary assessment is the approach to gathering survey data from individuals in real time in the individuals' real environment. Our study will be surveying individuals at different intervals, making it similar to an EMA approach.

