BCN is not intended to function as a medical device. BCN does not meet the software definition of a medical device as clarified in the updated 2019 *FDA Policy for Device Software Functions and Mobile Medical Applications Guidance for Industry and Food and Drug Administration Staff*. Section 201 (h) of the FD&C ACT defines a medical device as "...an instrument, apparatus, implement, machine, contrivance, implant, *in vitro* reagent, or other similar or related article, including any component, part, or accessory", that is "... intended for use in the diagnosis of disease or other conditions, or in the cure, mitigation, treatment, or prevention of disease, in man ..." or "... intended to affect the structure or any function of the body of man or other animals..." and "does not include software functions excluded pursuant to section 520(o) of the FD&C Act." (<https://www.fda.gov/regulatory-information/search-fda-guidance-documents/policy-device-software-functions-and-mobile-medical-applications>).

BCN is intended to be used as a mobile application that helps facilitate communication between caregivers and members of a patient's treatment team. It is not a treatment onto itself.

3.1.3 Feasibility will be measured 5 different ways:

- 1) Completion rate of the NPI-Q through the BCN app by the aMCI or AD caregiver over the 6-month intervention period.
- 2) Quantitative answers to the burden of scale completion question will be asked every time the NPI-Q is completed. *"How burdensome was completion of the prior scale (Answer options: not at all burdensome, mildly burdensome, moderately burdensome, or extremely burdensome)"*.
- 3) Completion rate of the semi-structured BPSD phone questionnaires triggered by "clinically significant" symptoms entered by the caregiver into the BCN application.
- 4) aMCI and AD Caregiver Feasibility and Usability Survey (3mo, 6mo, quantitative).
- 5) aMCI and AD Caregiver Feasibility and Usability Semi-Structured Interview (3mo, 6mo, qualitative).

3.1.4 Usability will be measured 3 different ways:

- 1) System Usability Scale
- 2) aMCI and AD Caregiver Feasibility and Usability Survey (3mo, 6mo, quantitative)
- 3) aMCI and AD Caregiver Feasibility and Usability Semi-Structured Interview (3mo, 6mo, qualitative)

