Response to Clinically Significant BPSD	
 Automatic free response follow up questions (via BCN). Automatic notification of research team. Automatic notification of SECBCI clinical team. The research team to contact the caregiver and complete a semi-structured interview and the Caregiver & Environment Assessment for Neuropsychiatric Symptoms. The research team member documents findings and notifies PI and SECBCI clinical team.
BCN Triggered Free Response Follow Up Questions	
 Please describe the behavior or symptom that is most distressing to you. What about this behavior or symptom makes it distressing to you? Why is it distressing? Please describe anything that you think may have led to the behavior or symptom. Describe anything you tried to address the behavior or symptom. Did it help?

Figure 1. Flow Diagram for The MOMENT RCT

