 - 12) Provision of a \$10 Kroger gift card to both the patient and caregiver following completion of the baseline visit activities.
 - 13) Provision of an Eskenazi Health parking voucher (only if the visit takes place in-person).
- The caregiver in the intervention group will be asked to complete a survey on Behavioral and Psychological Symptoms of Dementia (BPSD) for the person with aMCI or AD for 6 months through either the caregiver's smartphone or a loaner smartphone from the study. The survey is a mobile health version of the

Neuropsychiatric Inventory – Questionnaire (NPI-Q) delivered by the Brain CareNotes (BCN) app. The following additional survey question will be asked following delivery of the NPI-Q, *“How burdensome was completion of the prior scale? (Answer options: not at all burdensome, mildly burdensome, moderately burdensome, or extremely burdensome)”*

- Clinically Significant BPSD will be defined as when any NPI-Q severity domain = 3 regardless of caregiver distress, or whenever NPI-Q caregiver distress is marked as “moderate” “severe” or “very severe”.
-
- When Clinically significant BPSD is present at either the baseline visit, 3-month visit, final (6-month) visit or through completion of a BCN app record then the following actions will be triggered:
 - 1) Automatic free response follow-up questions (via BCN).
 - 2) Automatic notification of study team.
 - 3) Automatic notification of SECBCI clinical team.
 - 4) The research team to contact the caregiver and complete a semi-structured interview and the Caregiver & Environment Assessment for Neuropsychiatric Symptoms.
 - 5) The study team member documents findings and notifies PI and SECBCI clinical team.
- If the participants choose to complete their assessment in person then the study team will call 24-48 hours before the 3-month visit to make sure that in the past 2 weeks the patient and caregiver have not been in contact with anyone diagnosed with COVID-19, and have not developed any symptoms to suggest that they currently have COVID-19. If they choose to complete their assessment over the telephone, then the study team will not make this call.

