8.0 Study Calendar

A detailed table of study activities is listed below.

Table 4. Schedule of Study Activities

Schedule of Study Activities	Baseline Visit Within 14 days of enrollment	3-mo Within 14 days of scheduled target date	Final Visit (6-mo) Within 14 days of scheduled end
Provision of Study Information	X		
Completion of Informed Consent and HIPAA Consent	X		
Installation of BCN on loaner or caregiver phone	X		
Provision of BCN instructions	X		
Provision of Education on BPSD	X	X	X
COVID-19 Symptom Screener	X	X	X
Collect/Administer the following:			
COVID-19 Physical & Mental Health Questionnaire	X	X	X
Single Item Literacy Screener (SILS)	X		
Dyad Demographics	X		
NPI-Q	X	X	X
PSS-14	X	X	X
ZBI	X	X	X
Motivators and Barriers Survey	X		
Caregiver Pre-Intervention and Phone Semi-Structured Interview*	X	X	X
Caregiver & Environment Assessment of Neuropsychiatric Symptoms (CEAN)*	X	X	X
BCN app - Task Completion Burden Questions*	X	X	X
BCN app - Free Response Follow-Up Questions*	X	X	X
Data from EMR	X	X	X
Senior Technology Acceptance Scale	X	X	X

System Usability Scale (SUS)		X Intervention group only	X Intervention group only
Caregiver Post-intervention Survey		X Intervention group only	X Intervention group only
Caregiver Post-Intervention Semi-Structured Interview			X
Loaner phone retrieved or BCN app uninstalled from the caregiver phone			X
Provision of a \$10 Kroeger gift card to Caregiver	X		X
Provision of a \$10 Kroeger gift card to Caregiver	X		
Provision of a parking voucher, only if visit is conducted in-person	X	X	X

* Triggered by Clinically Significant BPSD

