12.0 Statistical Considerations and Analysis

12.1 AIM 1: Quantitatively and qualitatively, determine the feasibility of collecting responses on an EMA version of the Neuropsychiatric Inventory Questionnaire (NPIQ-EMA) from caregivers using smartphone technology at differing frequency intervals weekly or monthly, or a control group with data collected without the mobile health version and only at baseline and 6 month).

H1: Caregivers in the intervention groups will complete the assessments via smartphone and report an acceptable response burden. We anticipate that the response burden will be comparable to data collected in routine office visits.

Analysis H1: The primary outcomes for AIM 1 are feasibility and usability.

Feasibility will be measured 5 different ways:

- 1) Completion rate of the NPIQ-EMA over 6 months
- 2) Answers to the NPIQ-EMA response burden question every time the NPIQ-EMA is completed: "How burdensome was completion of the prior scale (Answer options: not at all burdensome, mildly burdensome, moderately burdensome, or extremely burdensome)"
- 3) Completion rate of the semi-structured phone interviews triggered by "clinically significant" symptoms
- 4) Post-intervention survey (quantitative)
- 5) Post-intervention semi-structured interview (qualitative) occurring immediately at the end of 6 months.

Usability will be measured in 3 different ways post-intervention:

- 1) System usability scale (SUS) total score
- 2) Post-intervention survey (quantitative)
- 3) Semi-structured phone interview (qualitative).

Quantitative Analysis: For quantitative analyses, there scores are continuous scale scores. Therefore, the intervention group feasibility scores will be compared to the control group's feasibility (response burden question) relative using ANCOVA to adjust for baseline characteristics including baseline demographics. The adjustment for baseline will increase precision and will statistically ensure comparability of the baseline level symptoms, even though random assignment should generally provide approximate comparability across a host of baseline characteristics.

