16.0 Other

16.1 Essential Equipment: We will use the Android Pixel phone by Google as a loaner phone for study subjects (caregivers) who do not have their own smartphone. The phone will be pre-loaded with the EMA version of the NPI-Q delivered by mobile app.

16.2 Potential Problems and Alternative Strategies:

16.2.1 Worsening caregiver burden: One concern of this proposal, is whether EMA monitoring of BPSD creates too much of a burden on the already burdened caregiver. Participants in our 28-day R01 study and in our pilot have not found the EMA pinging of the smartphone to be burdensome. The R01 study population demographics overlap significantly with our anticipated patient-caregiver population. As a safeguard, we will use usability and burden questions from the semi-structured interview from the initial 10 aMCI/AD caregiver-dyads to determine if the burden of answering EMA questions for the caregivers is too great. If that does turn out to be the case we will consider lengthening the surveillance interval or shortening the assessment battery.

16.2.2 Drop off in participation during the monthly response interval: It is possible that participation in the EMA BPSD surveillance might drop off during the two-month block, where BPSD surveillance takes place monthly instead of weekly. To address the potential, drop off in participation during the monthly surveillance block we will observe attrition rates for our first 10 dyads. If attrition rates exceed that of 17% we will make an adjustment to surveillance frequencies dropping the monthly surveillance block and instead continuing with weekly surveillance.

16.3 Summary and Future Directions: The following study looks to improve the care of aMCI/AD patient-caregiver dyads through the study of a BPSD surveillance intervention. Our choice of a weekly/monthly frequency, was a conservative approach in this early work to manage caregiver and provider burden but should evidence indicate high feasibility and value of weekly intervals, a future project could test higher frequencies to identify a frequency of diminishing return. Findings from this study will be used to develop a BPSD surveillance EMA intervention for a future R01 proposal that will improve the access to care and health of AD patient-caregiver dyads. This work will help my maturation into an independently funded investigator.

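### The repeated burden question rates only the NPI-Q, so Aim 1's quantitative rating cannot show how burdensome the triggered interviews are in weekly versus monthly months

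*Combined protocol and SAP*

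**What the plan says.** **Trigger.** Table 2 and Section 7.0 set the threshold at any NPI-Q domain scored 3 for severity, or caregiver distress of moderate or worse. This is a level, so a symptom need not be new or worse to meet it. Section 7.0 says that when it is met at a visit or "through completion of a BCN app record then the following actions will be triggered". Among the actions listed is: "The research team to contact the caregiver and complete a semi-structured interview and the Caregiver & Environment Assessment for Neuropsychiatric Symptoms". No section says that a repeat of the same symptom is handled differently.

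**Burden question.** Feasibility measure 2 (Sections 3.1.3 and 12.1) asks "How burdensome was completion of the prior scale", with four answer options, each time the NPI-Q is completed. Section 7.0 likewise places it after the NPI-Q. Of that scale, Section 3.1.1 says: "On average the NPI-Q takes 5 minutes to complete".

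**Analysis.** Section 12.1 compares the arms on "feasibility (response burden question) relative using ANCOVA to adjust for baseline characteristics". No other Aim 1 score is named for that comparison.

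**Other feasibility measures.** Measure 3 is described as "Completion rate of the semi-structured phone interviews triggered by" clinically significant symptoms. Measures 4 and 5 are a caregiver survey and a semi-structured interview, placed at 3 and 6 months in Section 3.1.3.

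**Safeguard.** Section 16.2.1 uses interview responses from the first 10 dyads to "determine if the burden of answering EMA questions for the caregivers is too great".

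**Schedule.** In Table 4 the row "BCN app - Task Completion Burden Questions" carries the asterisk that the footnote explains as triggered by clinically significant BPSD.

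**The concern.** The trial asks whether app surveillance is feasible and how often it should be done, with surveillance paired with a response to significant symptoms. For a caregiver who reports such symptoms, the experience is a short questionnaire plus a research call with an interview and the CEAN. The number of calls rises with the surveillance frequency. The only burden rating repeated within each condition concerns the questionnaire.

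Weekly surveillance could therefore be rated acceptable on measure 2 while the calls it generates go unrated. Section 16.3 says that high feasibility and value at weekly intervals could lead to testing higher frequencies, so the gap bears on the next study.

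The Table 4 asterisk is a separate, smaller matter. If staff or the app build followed it, a primary feasibility measure would be collected only on records that cross the threshold.

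**Working it through.** The plan gives no figure for contact load, so there is none to reproduce. The sample size plays no part, except that 64 analyzable and 77 enrolled intervention dyads (Section 12.4) are used in step 4.

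**1. Records per caregiver.** Inputs: six one-month periods (Section 5.0), alternating weekly and monthly (Table 1), so three of each. Assumptions: 4 records per weekly month, 1 per monthly month, all completed.

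- Weekly months: 3 × 4 = 12
- Monthly months: 3 × 1 = 3
- Total: 15

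Using 30/7 records per weekly month gives 3 × 30/7 = 12.9 and a total of 15.9.

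**2. App-triggered contacts.** Let *p* be the share of records over the threshold. The documents do not give it; the values below are assumptions.

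| *p* | Weekly months (12*p*) | Monthly months (3*p*) | Total (15*p*) |
|---|---|---|---|
| 20% | 2.4 | 0.6 | 3 |
| 50% | 6 | 1.5 | 7.5 |
| 100% | 12 | 3 | 15 |

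The ratio 12*p* / 3*p* = 4 does not depend on *p*, provided *p* is the same in both conditions. Controls have no app and so have no app-triggered contacts. They can trigger only at visits, where the CEAN and a semi-structured interview are already scheduled for both arms.

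**3. What each measure can say about the contacts.**

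| Measure | Covers the triggered contact? | Separable by condition? |
|---|---|---|
| 1. NPI-Q completion in the app | No | Yes |
| 2. Burden question | No, only the preceding scale | Yes |
| 3. Completion of triggered interviews | Whether it took place, not how burdensome it was | Yes, if each trigger is dated |
| 4. Survey | Possibly; items not shown | No |
| 5. Semi-structured interview | Possibly; items not shown | Not by design |
| Zarit, PSS-14 | Caregiving burden and stress, not study contacts | No; visits only |

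The "no" entries for timing follow from the alternation. By month 3 a caregiver has had weekly-monthly-weekly or monthly-weekly-monthly, and by month 6 three months of each. Neither visit follows exposure to one condition alone. No planned measure gives a quantitative rating of the contact by condition.

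**4. Table 4 read literally.** The burden question would be asked on a share *p* of records instead of all of them.

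- *p* = 20%, 64 dyads: 0.20 × 15 × 64 = 192 of 15 × 64 = 960
- *p* = 50%, 77 dyads: 0.50 × 15 × 77 = 577.5, about 578 of 15 × 77 = 1,155

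Those would be the records with the worst symptoms or distress.

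**The case against.** The strongest reply is that H1 is about completing the smartphone assessments, so a question about the scale fits the hypothesis. Aim 1 also has five feasibility measures. Measure 3 counts calls that do not take place, and the survey and interview may ask about calls. This stands against any claim that Aim 1 omits the contacts altogether: a reader might infer that, but with the survey and interview items not shown the documents cannot support it. It does not supply a quantitative rating of the contacts by condition.

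A reader might also infer that the first-10-dyad check offers no remedy that reduces calls. It does. Section 16.2.1 allows a longer surveillance interval, which lowers the number of records and hence of triggered calls, or a shorter battery. Table 1 allows the frequencies to change on feedback from the first 10 intervention participants. Distress from completing the intervention and withdrawals from discontent are monitored too (Sections 9.2 and 10.7). What remains is that the check in 16.2.1 is framed around answering the app questions.

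The missing repeat rule is not an error either. Responding to every record over the threshold is a rule that staff can carry out. Limiting full interviews to one per month would give weekly and monthly months the same number of full responses for a lasting symptom, which could blunt the contrast in H3.

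The Table 4 asterisk may be a labelling slip. It also sits on the CEAN and interview rows, which Section 7.0 schedules at visits. That makes the literal reading less likely, but the conflict is still worth removing.

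**Conclusion.** The point holds as a limited gap in measurement. Up to about 12 interview-and-CEAN contacts in weekly months and 3 in monthly months can arise per caregiver, and the repeated burden question rates none of them. Those maxima assume 4 records per weekly month, full completion and a symptom over the threshold at every record. The fourfold ratio assumes only 4 records per weekly month, equal completion and an equal trigger share. The length of a contact is not given, so the load is not converted into time here.

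A reader might conclude that the between-arm ANCOVA is biased. The documents do not support that: it compares ratings of the same scale and is a valid target if described as NPI-Q burden only. No bias in measure 3 is shown either. Its unstated denominator and time window are missing detail in a descriptive measure.

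The Table 4 conflict is real on the page and should be corrected whichever reading was intended.

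**What to change.** 1. At the end of each triggered call, ask the same four-option burden question about the contact. Report it descriptively beside measure 2, by weekly and monthly condition. Because only caregivers who complete the call can answer, report with it the share of triggered calls declined or not reached. Include the rating in the first-10-dyad check in Section 16.2.1.
2. In Section 12.1, describe the between-arm ANCOVA as a comparison of NPI-Q burden only. The new item does not enter it.
3. Remove the asterisk from the burden-question row of Table 4, so that the question follows every NPI-Q as Sections 3.1.3, 7.0 and 12.1 state.

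The cost is one extra question per triggered call (3 to 15 per caregiver over six months across the trigger shares shown), a record of each call's outcome, and protocol wording. No visits or participants are added.

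Optional clarifications, not part of this point: whether a repeat trigger gets the full interview, the denominator and contact window for measure 3, and how the treatment-team contact in Table 1 relates to the research-team contact in Table 2.

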6.0 Enrollment/Randomization

6.1 Patient Population and Setting: Our research center has 20 plus years of experience developing interventions to improve the care of older adults with AD and their caregivers. The PREVENT study applied the concepts of collaborative care to persons with AD in the primary care setting in a safety-net hospital system with in Indianapolis, IN⁴³. At 12 and 18 months, results of the PREVENT study demonstrated improvements in BPSD frequency and caregiver distress from BPSD⁴³. The results and experiences with PREVENT, as well as subsequent work by our research team and others led to the creation of the Sandra Eskenazi Center for Brain Care Innovation. This memory care practice serves as both a diagnostic and longitudinal care center for persons living with dementia and their family caregivers.

6.2 Preliminary Work: Neuropsychiatric Inventory Questionnaire (NPI-Q) –

Ecological Momentary Assessment (EMA) Caregiver Pilot: We successfully pilot tested the NPIQ-EMA app in four AD patient-caregiver dyads without any attrition. The time horizon for the pilot differs from the proposal in that the caregiver was asked to fill out the smartphone survey (NPIQ-EMA) daily for a 2-week time period. Patient ages ranged from 63 to 95, and caregiver ages ranged from 63 – 82. Three of four caregivers identified as African American. All four caregivers found answering the NPIQ-EMA questions to “Not be burdensome.” Several caregivers reported that the NPIQ-EMA improved their awareness of the patient’s BPSD. Three of four answered that they would prefer weekly monitoring rather than daily and the last caregiver expressed a preference for daily monitoring. All caregivers agreed that the system was easy to use.

6.3 Recruitment, Screening, Informed Consent, and Enrollment: The Sandra Eskenazi Center for Brain Care Innovation provides longitudinal care to ~ 600 patients; 38.7% are Black; and 70.4% are female. In addition, each of five clinicians completes an initial assessment on 1-3 new patients per week. We anticipate a recruitment number of 154 dyads over 27 months and believe this to be achievable. Half of the dyads would be randomized to the intervention or treatment as usual group. Our group has a recruitment rate of approximately 50% of eligible subjects in this environment⁴³.

6.4 Randomization Scheme: Participating dyads will be randomized to the two groups (intervention vs control) using a randomization list that contains group assignment in blocks, thus ensuring that the groups have comparable sample sizes throughout the study. We will use a stratified block random assignment following the Kernan strata determination formula (Kernan et al. 1999) listed as, $\# \text{ of strata} < n / B \times 4$, where B is block size and “... n is the sample size at the first planned interim analysis and 4 is a safety factor that accounts for unequal distribution of patients among strata.” Using $n=154$ and $B=4$, then, the $\# \text{ of strata} < 9$. In this study, we will use 8 strata = 2 Diagnosis (aMCI, AD) x 2 Gender (M, F) x Age (< 65, \geq 65). Sealed envelopes with randomization assignments will be prepared by a research team member not involved

with enrollment. Sealed envelope preparation will follow calculations and instructions made by the study biostatistician.

Participants in the intervention group will be further randomly assigned to start with 1 of 2 schedules of EMA surveillance frequency (1) weekly or (2) monthly. The intervention participants will then cross-over each month between the two surveillance frequency conditions, yielding 6 periods for their 2 x 6 cross-over design.

6.5 Potential Sources of Biological Variation and Co-variates: The experimental design allows us to explore moderators of response.

Table 3. Baseline Potential Sources of Variation

Subject	Obtained from caregiver	Obtained from EMR
amCI/AD Subject	Sex , age, race, ethnicity, education level, medical status, insurance type	Age, diagnosis, cognitive function, physical function, illness severity, problem list & med list
Caregiver Subject	Sex , age, race, ethnicity, education level, relationship to person with amCI/AD, # of hours caregiving, caregiver burden, and perceived stress	None

